2 SAMPLE SIZE

2.1 Power to demonstrate non-inferiority in the primary efficacy outcome (primary objective relating to Regimens B and C)

Stage 2 aimed to randomise at least 200 patients to each of Regimen B (B_{mox} or B_{lev}) and Regimen C. This revised sample size in protocol version 8.0 was determined based on the assumption that the proportion of patients with a favourable efficacy outcome at Week 76 is 80% for Regimen B (estimated based on preliminary Stage 1 results) and 82% for Regimen C (based on an anticipated minimum benefit in efficacy of using 40 weeks treatment with bedaquiline compared to 16 weeks treatment with kanamycin). Using a non-inferiority margin of 10% and a one-sided significance level of 2.5%, 172 evaluable patients will be required in each of the two regimens to demonstrate non-inferiority of Regimen C to Regimen B with 80% power. To account for 14% of patients excluded from the primary per protocol efficacy analysis population, a total of 400 patients will need to be enrolled across the 2 regimens.

A sample size of 400 patients enrolled to the comparison of Regimens B and C is necessary to rule out an 8% increased mortality in Regimen C compared to the 8% observed on Regimen B in the preliminary analysis of STREAM Stage 1. This will provide 80% power with a one-sided 0.025 type I error.

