6.2 Tabulation of primary endpoint classification

Since the primary endpoint is a composite of various components, the actual reason (component) for outcome will also be tabulated by treatment arm. Patients will be classified by the first event that made the patient unfavourable (see section 3.2) and further subclassified by whether their outcome is deemed to be bacteriologically related or not, based on a review of all data up to the time that the outcome occurred (see Section 6.2.1).

6.3 **Subgroup analyses**

This primary efficacy analysis will be repeated (in both mITT and PP analysis populations) in subgroups according to the following baseline characteristics:

- HIV infection status
- baseline drug resistance patterns (i.e. resistance to pyrazinamide and isoniazid)
- albumin levels (by severity grade)
- BMI (<16.0 kg/m², 16.0-18.4 kg/m², 18.5-24.9 kg/m², >25 kg/m²)
- cavitation (presence, absence)
- study centre/country
- age (<25, 25-<45, ≥45)

- sex
- Smoking history (current, ex, never)
- Smear grade
- Weight band (<33kg, 33-50kg, >50kg)
- Race.

6.4 **Sensitivity analyses**

The primary efficacy analysis will be repeated:

- A. Unadjusted for any covariates except randomisation protocol.
- B. Adjusted for randomisation stratification factors HIV status and centre. Small strata with fewer than 10 patients will be combined within geographical regions within country.
- C. Adjusted for randomisation stratification factors and any additional important covariate such as cavitation at baseline, baseline bacillary load or adherence.
- D. Ignoring substitutions of levofloxacin for moxifloxicin and vice versa when counting the number of drug substitutions within the definition of unfavourable outcome.
- E. Ignoring starting linezolid alone as a criterion for an unfavourable outcome.
- F. Reclassifying any participants with reinfection (based on genotype or DST) as "non-assessable" rather than unfavourable.
- G. Reclassifying any participants who died as a result of trauma (as adjudicated by independent review) as "non-assessable" rather than unfavourable.
- H. Reclassifying any participants with missing Week 76 culture results because of COVID-19 as "non-assessable" rather than unfavourable.
- Reclassifying any participants with missing Week 76 culture results because of COVID-19 as favourable if they meet the definition of favourable, with the latest of the 2 negative culture results being within the Week 68 window, unfavourable otherwise.

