The assumption of proportional hazards between the two comparisons will be tested using the proportional hazards test based on the Schoenfeld residuals after fitting the Cox Proportional Hazards models. In the case where there is adequate evidence that the proportional hazard assumptions are violated at the 5% level (i.e. p<0.05), methods where proportional hazards is not a necessary assumption will be used, such as the Wilcoxon test of equality of survivor functions and restricted mean survival time.

Sensitivity analyses will be conducted i) considering different dichotomies of the 5 point scale and ii) assessing the assumption of independent or non-informative censoring (i.e. that the likelihood of an FoR event at the time of censoring is assumed to be the same as for those in whom no censoring occurred) using inverse probability of censoring weights (IPCW)⁸ and multiple imputation(MI)⁹ respectively.

This failure or recurrence analysis will be repeated in subgroups according to baseline characteristics as described in Section 6.3.

7.1.4 Favourable outcome at Week 132

A patient's outcome will be classified as favourable if their last two sputum culture results are negative, unless they have previously been classified as unfavourable. These two sputum results must be from samples taken at separate visits; the latest must be no more than six weeks before their scheduled last efficacy visit (see Section 7.1).

A patient's outcome at their scheduled last efficacy visit will be classified as unfavourable if:

- They are unfavourable at Week 76
- They start any MDR-TB treatment between their Week 76 and scheduled last efficacy visits
- They die between their Week 76 and scheduled last efficacy visits
- At least one of their last two culture results, from specimens taken on separate occasions, is positive.

A patient who does not have a culture result within the window for their scheduled last efficacy visit, having not otherwise been classified as unfavourable, will be regarded as non-assessable if their last two cultures, from specimens taken on separate occasions, are negative. All other patients who do not have a culture result within the window for their scheduled last efficacy visit and do not meet this definition of non-assessable will be classified as unfavourable.

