A sensitivity analysis will estimate the proportion unfavourable at Week 132 on the subset of participants randomised at least 132 weeks on or before 30 November 2021 (see Section 6.1.1). For this analysis, non-assessable participants will be excluded. The mITT population will be primary and the PP and mPP populations will be sensitivity analyses.

The above analyses will be repeated for the following comparisons, restricting the population in each case to include only concurrent controls within sites: Regimen B_{lev} and Regimen C, Regimen B_{mox} and Regimen D and Regimen B, Regimen B and Regimen A, Regimen C and Regimen A, Regimen D and Regimen A. The analysis will also be repeated (in both mITT and PP analysis populations) in subgroups according to HIV status.

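### SAP 6.3 repeats the primary analysis within every level of 12 baseline characteristics, with no interaction test and no exploratory label

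*SAP*

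**What the plan says.** SAP 6.3 says: "This primary efficacy analysis will be repeated (in both mITT and PP analysis populations) in subgroups according to the following baseline characteristics". Its 12 bullets are HIV status, drug resistance (pyrazinamide and isoniazid), albumin grade, BMI, cavitation, centre/country, age, sex, smoking, smear grade, weight band and race.

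The analysis being repeated is defined in SAP 6.1.1: a difference in favourable proportions using Cochran-Mantel-Haenszel weights, with 95% confidence intervals and p-values. The 10% decision rule is stated separately, in SAP 6.1.2, for the overall B versus C comparison.

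Two later sections also use subgroups. SAP 7.1.3 reuses the whole list: "This failure or recurrence analysis will be repeated in subgroups according to baseline characteristics as described in Section 6.3". SAP 7.1.4 does so for one factor only: "The analysis will also be repeated (in both mITT and PP analysis populations) in subgroups according to HIV status".

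Neither document plans a test of treatment-by-subgroup interaction for efficacy. SAP 7.4, on multiple testing, discusses outcomes and does not mention subgroups. The SAP does use the word exploratory elsewhere: for the Bayesian analysis (6.5), for Section 8, and for the C versus D comparisons up to Week 76. It does not use it in 6.3. For Stage 2, protocol 11.6 names subgroups only for grade 3 or greater adverse events, so it does not fill the gap.

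**The concern.** A subgroup analysis asks whether the B–C difference varies with a baseline characteristic. A p-value or interval computed inside one level asks whether the difference in that level is zero, which is another question. One level can be significant and its neighbour not, although the two effects are compatible.

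With many levels, some will show a difference by chance. With small levels, intervals will be wide and will often cross 10 points whatever the truth. The list includes factors that guideline writers look at, such as HIV status, BMI, resistance and country. A chance result or a wide interval could be taken as evidence for or against Regimen C in such a group, and the SAP gives the reader no caution.

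**Working it through.** **Inputs.** From SAP Section 2: "Using a non-inferiority margin of 10% and a one-sided significance level of 2.5%, 172 evaluable patients will be required in each of the two regimens". Target power is 80%. The assumed favourable proportion "is 80% for Regimen B (estimated based on preliminary Stage 1 results) and 82% for Regimen C". Also: "To account for 14% of patients excluded from the primary per protocol efficacy analysis population, a total of 400 patients will need to be enrolled". The number and size of levels are not given for albumin grade, smear grade, centre/country or race, so they are assumed below.

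**Step 1. Reproduce the plan's figure.** n per arm = (1.96 + 0.8416)² × (0.80×0.20 + 0.82×0.18) / (0.10 + 0.02)² = 7.849 × 0.3076 / 0.0144 = 167.7, so 168. The plan states 172, which is 2.3% apart and gives 81% power by the same formula. For enrolment, 2 × 172 = 344 and 344 / (1 − 0.14) = 400. The plan's figures reproduce.

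**Step 2. Chance differences when the regimens are equal.** SAP 6.1.1 does not say which null its p-value tests, so I count a level as different when its 95% interval excludes zero.
- Treating k levels as independent, the chance of at least one is 1 − 0.95^k: 79% for 30 levels and 87% for 40. The same patients appear under every factor, so these are only a guide.
- Simulation: 2,000 trials, both arms at 80%, 13 independent factors with 42 levels of assumed size, crude Wald-type intervals, and levels with fewer than 5 patients in either arm skipped. At least one interval excluded zero in 78% of trials, at both 172 and 200 per arm.
- A second simulation (3,000 trials, 172 per arm, about 40 levels, levels under 10 per arm skipped) gave 77%.

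**Step 3. The 10% margin, if it were read within a subgroup.** Chance of meeting it = Φ[(0.10 − (pB − pC)) / SE − 1.96], with SE = √[pB(1 − pB)/n + pC(1 − pC)/n]. For a half-size subgroup of 172 per arm with both arms at 80%: n = 86, SE = √(0.32/86) = 0.0610, and Φ(1.64 − 1.96) = 37%.

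| Share of trial | n per arm (of 172 / of 200) | Both arms 80% | B 80%, C 82% |
|---|---|---|---|
| Whole | 172 / 200 | 64% / 71% | 81% / 86% |
| Half | 86 / 100 | 37% / 42% | 52% / 58% |
| Third | 57 / 67 | 27% / 30% | 37% / 42% |
| Quarter | 43 / 50 | 21% / 24% | 29% / 33% |
| Tenth | 17 / 20 | 11% / 12% | 14% / 16% |

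With equal arms, an even chance needs 0.32 × (1.96/0.10)² = 122.9 per arm. That is 61% of a 200-per-arm trial and 71% of a 172-per-arm trial. This table depends on the share of patients in the subgroup, not on the assumed list of levels.

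**Step 4. What interaction tests would bring.** One test per factor at 5%, taken as independent: 1 − 0.95¹³ = 49% chance of at least one false positive (46% with 12 factors). The simulation gave 49–50%.

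**The case against.** The strongest reply is that 6.3 refers back to estimation and not to a decision. SAP 6.1.1 describes estimating the difference; the margin rule has its own heading in 6.1.2, and protocol 11.4.1 treats only the overall B versus C comparison as primary. This stands. A reader might infer that equal regimens will fail non-inferiority in most subgroups. That follows only if the margin is applied there, which 6.3 neither says nor excludes.

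A reader might also infer that a false subgroup difference is near certain. The calculations do not support that: about 78% when levels are read one by one, and about 49% with 13 interaction tests. Only a loose criterion, some level with a point estimate at least 10 points against C, reaches about 95%. Nor do the two populations double the number of tests, because PP is a subset of mITT (SAP 4.4).

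It is also fair that the simulation rests on assumed level sizes, independent factors and crude intervals in place of the planned stratified analysis. The 172 is the per-protocol planning figure, and protocol 11.4.1 expects fewer exclusions from mITT. SAP 1.6 has a fallback for sparse strata, but it concerns stratification and not which subgroups can be interpreted. The Extensive Stage 2 SAP is not available here; the Core SAP does not refer subgroups to it, as it does for PK/PD.

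Finally, interaction tests have false positives of their own, and intervals by level would still be shown. Both are true. They are reasons for an exploratory label and a no-claims sentence, not for keeping within-level p-values, which cannot show whether effects differ.

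**Conclusion.** The concern holds as a weakness in how the subgroup analyses are specified and could be read. SAP 6.3 plans within-level inference over 12 or 13 characteristics in two populations, without the test that answers the subgroup question and without a label limiting interpretation. SAP 7.1.3 inherits the full list; 7.1.4 is affected for HIV status only.

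The 78% rests on about 40 levels of assumed size and on both arms being 80% favourable. The margin figures rest on the 80% rates and the normal approximation, and they matter only if someone applies the 10% rule inside a subgroup.

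A reader might infer that the subgroup list inflates the error rate of the trial's main conclusion. It does not: the primary non-inferiority test is a single overall comparison, and its type I error is unaffected.

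**What to change.** Amend SAP 6.3, and the related text in 7.1.3 and 7.1.4, to say that:
- subgroup analyses are exploratory;
- for each factor, the B–C difference (hazard ratio for time to failure or recurrence) and 95% confidence interval are shown by level, without within-level p-values;
- one treatment-by-factor interaction test is reported per factor, on the risk-difference scale, or on the log-hazard scale for time to failure or recurrence;
- the 10% margin is not applied within subgroups, and no claim of non-inferiority or superiority is made from them.

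The cost is wording and one test per factor, with no new data. There are three downsides. Interaction tests have low power, so a null result is not evidence of a uniform effect. Thirteen of them at 5% carry the 49% false-positive chance shown above, which is why the label is needed. And SAP v6.0 (September 2022) describes work at the time of the primary analysis in the past tense, so for Week 76 the change has to be reported as post hoc.

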All positive isolates, except those of week 4, will be sent to the designated study reference laboratory, to confirm species identification and susceptibility status. This includes diagnostic strains and recurrence strains, in case of failure or relapse besides isolated positive cultures in-between successive negatives. Strains from recurrences will be tested for DST as well as fingerprinting, to confirm their identity and to compare their resistance pattern with the originally isolated strain. The reference laboratory will store all study strains at -80°C and local laboratories will store at -20°C.

The techniques to be used at the reference laboratory are:

- Slow phenotypic DST using the proportion method on Löwenstein-Jensen medium for first line drugs and agar-based Middlebrook 7H11 medium for second line drugs; for difficult strains, the minimum inhibitory concentration (MIC) and DNA sequencing can be used to arrive at the most correct result
- Fingerprinting; MIRU-VNTR analysis (mycobacterial interspersed repetitive units—variable number of tandem repeats).

A detailed description of the various laboratory tests is found in the STREAM Microbiology Manual.

Results of resistance tests undertaken by the reference laboratory are primarily for analysis purposes and will not be routinely provided to the sites. Treatment changes will not be suggested on the basis of these results unless a patient is not doing well and it is decided that a change of treatment is required.

However, if any patients are found to have XDR-TB (confirmed resistance to fluoroquinolones and second-line injectables from phenotypic DST) from samples collected at baseline, these results will be provided to sites, and the patients should be withdrawn from trial treatment and treated according to national guidelines.

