#### **Unfavourable**

A patient's outcome will be classified as **unfavourable** if:

- They are discontinued from their allocated study treatment and subsequently restarted on a different MDR-TB regimen.
- 2. Treatment is extended beyond the scheduled end of treatment for any reason other than making up days when no treatment was given (missed treatment) for a maximum of eight weeks. A maximum of 14 days of extra treatment (irrespective of reason) is acceptable before it is classified as treatment extension. In addition, if the intensive phase of treatment has been extended for delayed sputum conversion (maximum 8-week extension permitted) the scheduled end of treatment will also be extended by the same amount, in accordance with Section 7.3.2.
- 3. They are restarted on any MDR-TB treatment after the scheduled end of treatment, but before 132 weeks after randomisation for Stage 1 and before 76 weeks after randomisation for Stage 2.
- 4. They change their allocated study treatment for any reason other than (1) the replacement of a single drug\* or (2) for patients allocated to Regimen A when the change is as a result of changes in local guidelines and not related to any change in the patient's circumstances or condition.
- 5. Bedaquiline is started where the allocated regimen did not originally contain that drug (Regimen A or B)
- 6. A second line injectable agent is started in Regimen C.
- 7. A drug from the class of nitroimidazoles or linezolid is started.
- 8. They die at any point during treatment or follow-up.
- 9. At least one of their last two culture results, from specimens taken on separate occasions, is positive.
- 10. They do not have a culture result at Week 76 or thereafter for the Stage 1 comparison, or within the Week 76 window for the Stage 2 comparison.

11. The failure or recurrence specimen at or before the Week 76 window was a different strain to their randomisation specimen, i.e. re-infection (the Stage 2 comparison only).

Starting a single drug is not considered to be a substantial change to the regimen and therefore does not result in an unfavourable outcome, with the exception of adding bedaquiline (in Regimen A or B), a second-line injectable in Regimen C or a drug from the class of nitroimidazoles or linezolid (in any regimen).

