3.1.1 Extension of visit window due to the COVID-19 pandemic

The end dates of the Week 76 window will be extended for any Stage 2 patients whose Week 76 appointment is scheduled to occur during the COVID-19 pandemic and did not occur due to restrictions on movement, unacceptable risk of exposure to COVID-19 in connection with the scheduled visit, or any other reason related to the pandemic. For those patients, the Week 76 sputum samples must be taken in a window beginning six weeks prior to the scheduled visit date and ending within the Week 84 visit window i.e. within 14 weeks of the scheduled Week 76 visit date.

3.2 **Primary efficacy outcome**

The primary efficacy outcome measure is the proportion of patients with a favourable outcome (as defined below) at Week 76.

Only data from events occurring before the end of the Week 76 window will be included in the primary analysis of the primary efficacy outcome.

Culture results obtained using acidified Ogawa (Kudoh medium) will be used in the primary analysis, unless missing, when results from Löwenstein-Jensen (LJ) media will be used.

A positive culture is defined as at least one colony and a negative culture is defined as absence of growth (no colonies).

Favourable

A patient's outcome will be classified as **favourable** if their last two culture results are negative unless they have previously been classified as unfavourable. These two cultures must be taken on separate visits (on different days); the latest of which being within the Week 76 window.

Patients that don't have a culture result within the Week 76 window because they were unable to produce sputum or their sample was contaminated, will be classified as favourable if their last two cultures before the Week 76 window are negative and they have not previously been classified as unfavourable; such patients will be identified separately in tables.

Participants with no sputum sample available at Week 76 due to Covid-19 restrictions who are not otherwise classified as unfavourable will be considered unfavourable. Sensitivity analyses will reclassify these participants as i) non-assessable and excluded from the primary efficacy analysis, and ii) favourable if they meet the definition of favourable above, with the latest of the 2 negative culture results being within the Week 68 window, and unfavourable otherwise.

Unfavourable

A patient's outcome will be classified as **unfavourable** in Stage 2 if:

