7.1.3 Time to failure or recurrence

Favourable outcome for each participant will be re-classified according to the likelihood that it was a *Failure or Recurrence (FoR) event* on a five-point Likert scale: Definite, Probable, Possible, Unlikely, and Highly Unlikely⁷.

An event will be considered *Highly Unlikely* to be a FoR event only if there is evidence of durable cure; i.e. the primary outcome classification of favourable which required completion of follow-up with negative cultures. A *Definite* FoR event requires clear bacteriological evidence of failure or recurrence (excluding a proven reinfection with exogenous strain of *M. tuberculosis*), a *Probable* FoR event requires some evidence for failure or recurrence (clinical, bacteriological, or radiological) in the absence of clear bacteriology. The remaining participants will be classified as possible or unlikely based on their data. Time of the FoR event/censoring is the same as defined in the time to unfavourable outcome analysis (see Section 7.1.2). The FoR classification will reviewed by an independent clinician, blinded to treatment.

In the time to FoR analyses, the main groups of interest are those classified as having a Definite or Probable FoR event, with censoring of Possible, Unlikely and Highly Unlikely events at the time of the censoring event which met criteria for Unfavourable or Not Assessable in the primary analysis.

Median time to FoR will be calculated for Regimen B, Regimen C, and Regimen D using the Kaplan-Meier estimator.

A hazard ratio with corresponding two-sided 95% confidence intervals and p-value will be estimated for the comparison of Regimen B with Regimen C, and Regimen B with Regimen D. A Cox Proportional Hazards model will be used, adjusted for randomisation protocol (as defined in Section 1.6) and the stratification factor HIV status with the three categories of: HIV negative; HIV positive with CD4 count ≥350 cells/mm³; and HIV positive with CD4 count <350 cells/mm³.

The equality of survivor functions for time to failure or recurrence for Regimen B and Regimen C, and Regimen B and Regimen D, will each be tested using a Log rank test, stratified by randomisation protocol (as defined in Section 1.6) and the randomisation stratification factor HIV status with the three categories of: HIV negative; HIV positive with CD4 count ≥350 cells/mm³; and HIV positive with CD4 count <350 cells/mm³.

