9.2.3 Drug resistance

All drug resistance analyses will be based on phenotypic DST results unless unavailable when genotypic results will be used.

Drug resistance at screening or baseline will be tabulated by treatment arm.

Acquired resistance to any drugs will also be described and tabulated by treatment arm using i) the last available DST result for each drug for each patient, and ii) all available post-randomisation DST result (i.e. classifying as resistant if any result is resistant) for each drug for each patient ignoring isolated resistance unless it is the last result prior to the point of analysis. The proportion of participants developing resistance, especially resistance leading to the development of pre-XDR or XDR strains of TB in Regimen C and Regimen D will be compared to that in Regimen B for data up to Week 76, and for the Allocated treatment phase only (i.e. up to the point of starting a salvage regimen).

9.3 **Safety**

All the following analyses will be on the safety population.

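### Sensitivity analysis F lets a drug-susceptibility change alone count as reinfection, so a same-strain failure with acquired resistance could drop out of that analysis; separately, SAP 3.2 omits the protocol's reinfection criterion

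*SAP*

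**What the plan says.** **The sensitivity analysis.** SAP 6.4 item F repeats the primary efficacy analysis after "Reclassifying any participants with reinfection (based on genotype or DST") as non-assessable instead of unfavourable. It does not say which drugs count, whether resistance must be gained or lost, or what happens when typing is missing or disagrees with DST. Item F does not spell out what non-assessable means. For the COVID-19 reclassification, SAP 3.2 uses the same term as "non-assessable and excluded from the primary efficacy analysis", and I read F the same way.

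**Reinfection elsewhere.**
- Protocol 11.2.1, unfavourable item 11, makes a patient unfavourable in Stage 2 if the failure or recurrence specimen "was a different strain to their randomisation specimen, i.e. re-infection". It has no DST criterion and names no laboratory method.
- Protocol 8.7: "Strains from recurrences will be tested for DST as well as fingerprinting, to confirm their identity". The sentence continues with comparison of the resistance pattern with the first isolate. The listed typing technique is "Fingerprinting; MIRU-VNTR analysis".
- SAP 7.1.3 defines a definite failure or recurrence as one with clear bacteriological evidence, "excluding a proven reinfection with exogenous strain". An independent clinician, blinded to treatment, reviews the classification.
- SAP 3.3 handles reinfection by the composite strategy in both primary estimands.
- SAP 3.2 lists ten unfavourable criteria. Reinfection is not among them.

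**Acquired resistance.** SAP 9.2.3: "Acquired resistance to any drugs will also be described and tabulated by treatment arm", using post-randomisation DST results.

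**The concern.** A DST pattern that differs from baseline has two possible explanations: a new strain, or the original strain having acquired resistance. The first is reinfection. The second is a failure of the regimen. Because F joins its two criteria with an or, and gives no rule on direction of change, it cannot separate them.

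A patient who fails with the original strain and new resistance could then be a definite failure or recurrence under SAP 7.1.3, a case of acquired resistance under SAP 9.2.3, and a removed reinfection under F. If such removals were more common in one arm, F would flatter that arm. A sensitivity analysis meant to show that the result does not hinge on reinfections would instead be discarding some regimen failures.

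The missing criterion in SAP 3.2 is a separate matter. It concerns the primary endpoint itself, because the SAP's General Information says that the SAP supersedes the analysis plan written in the protocol.

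**Working it through.** **1. The design figure.** SAP 2.1 gives 172 evaluable patients per arm: 80% favourable on B, 82% on C, margin 10 points, one-sided 2.5%, 80% power. With unpooled variance:

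n = (1.96 + 0.8416)² × (0.80×0.20 + 0.82×0.18) / (0.10 + 0.02)² = 7.849 × 0.3076 / 0.0144 = 167.7, so 168 per arm.

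At 172 per arm the power is Φ(0.12/√(0.3076/172) − 1.96) = Φ(0.878) = 81.0%. Enrolment is 344/0.86 = 400. These agree closely with the plan, so 172 per arm is a fair basis for illustration.

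**2. What one removal does in F.** The documents give no number of reinfections or DST-only cases, and no figure for F. The counts below are assumptions. The interval is an unstratified Wald interval for B minus C; the plan's own analysis is stratified with Cochran-Mantel-Haenszel weights.

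Upper bound = (pB − pC) + 1.96 × √[pB(1−pB)/nB + pC(1−pC)/nC]

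Start with B 138/172 (80.23%) and C 135/172 (78.49%):

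- No removal: 1.74 + 1.96 × 4.363 = **10.30**; margin not met.
- One C failure removed (135/171 = 78.95%): 1.29 + 1.96 × 4.352 = **9.82**; margin met.
- Two C failures removed (135/170 = 79.41%): 0.82 + 1.96 × 4.340 = **9.33**.
- One B failure removed instead (138/171 = 80.70%): 2.21 + 1.96 × 4.350 = **10.74**; further from the margin.
- Two removed from each arm (138/170 and 135/170): 1.76 + 1.96 × 4.313 = **10.22**.
- Five removed from each arm (138/167 and 135/167): 1.80 + 1.96 × 4.227 = **10.08**.

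Each one-sided removal shifts the bound by roughly half a point, in a direction set by the arm it comes from. Balanced removal hardly shifts it. The starting counts were chosen close to the margin. With C also at 138/172, the bound goes from 8.42 to 7.92 when one C failure is removed, and the conclusion does not change.

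**3. Chance of F meeting the margin when C is truly 10 points worse.** With true rates of 80% and 70% and 172 per arm, removing 1, 2, 3 or 5 failures from C alone raises the chance that F shows non-inferiority from 2.5% to about 3.1%, 3.7%, 4.5% or 6.6%. This applies to F only, not to the trial's type I error.

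**4. Protocol item 11 against SAP 3.2.** Take a patient with a different-strain recurrence before the Week 76 window who is not retreated and whose last two cultures, the later one inside the window, are negative. Under protocol item 11 the patient is unfavourable. Under SAP 3.2 no criterion applies: no retreatment, no positive among the last two cultures, and a result in the window. The patient is favourable. SAP 3.3 and item F both presuppose the protocol's answer.

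**The case against.** F is one of twelve sensitivity analyses (A to L). Under SAP 6.1.2, non-inferiority rests on the primary analysis in both the mITT and PP populations, and reclassification under F changes neither. A reader might infer that the formal conclusion or its type I error is compromised by F; the documents do not support that.

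A reader might also infer that F will delete the worst failures. The text permits that but does not require it. F speaks of patients with reinfection, and whoever applies it could take only loss of baseline resistance as DST evidence. Working rules may sit in the Microbiology Manual or the Extensive SAP, which are not available here.

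A third tempting reading is that F favours Regimen C. Protocol 2.2.1 says acquired resistance may be more frequent on C and D, then calls the risk small. It cites a bedaquiline trial in which the six patients who developed pre-XDR or XDR infection were in the control arm and none were in the bedaquiline arm. On that pattern F would remove B failures and make non-inferiority harder to show.

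Finally, Protocol 8.7 plans both tests on recurrence strains, "to confirm their identity and to compare their resistance pattern with the originally isolated strain", so DST has a legitimate place. Failures with new resistance also stay visible through SAP 7.1.3 and 9.2.3.

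All of this limits the weight of the point. It does not supply the missing rule in F, and the independent blinded review that protects SAP 7.1.3 is not carried over to F.

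**Conclusion.** As worded, F allows a DST difference alone to establish reinfection. That is looser than the protocol's different-strain criterion and the SAP's own requirement of proof in 7.1.3, and it overlaps with what 9.2.3 counts as acquired resistance. The fault is confined to F.

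Its size cannot be stated, because the number of DST-only cases and their split between arms are unknown. One unbalanced removal is worth about half a point on the upper bound, which matters only when the result lies near the margin. This assumes that non-assessable means excluded in F, and that the unstratified interval approximates the planned one.

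The omission of item 11 from SAP 3.2 is a separate gap and does touch the primary endpoint. It should not be read as making reinfected patients favourable in general: those who are retreated, or who have a positive among their last two cultures, remain unfavourable under other criteria. It changes the outcome for the narrow case in step 4 of the working.

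**What to change.** - **SAP 6.4 F.** Define reinfection as a strain that differs from the baseline isolate on typing at the reference laboratory. Keep the patient unfavourable when typing is missing or when the only change is gained resistance. List DST-only cases by arm with the direction of change.
- **SAP 9.2.3.** Keep every resistance case in the table, and flag those typed as a different strain and those untyped. Requiring a strain match would drop resistance cases that have no typed pair.
- **SAP 3.2.** Restore protocol item 11, so that the list agrees with SAP 3.3 and with item F.

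The cost is wording and one derivation, since fingerprinting of recurrence strains is already planned. The downside is that a few true reinfections without a typed pair stay unfavourable in F. SAP version 6.0 is dated September 2022 and section 6.1.3 refers to the primary analysis in the past tense, so a change made now should be labelled post hoc and shown beside F as specified.
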